16.10 Interim Analyses

An interim analysis may be performed prior to completion of the study to support a potential regulatory submission.

16.11 Sample Size and Power

Open-label treatment period (initial 28-week period):

Approximately 240 sites are planned in 30-35 countries. The study will include eligible patients who have completed Visit 7 (Completion Visit) of the lead-in studies. Assuming a completion rate of 85% and that approximately 85% of these are eligible and complete the extension study, this results in a total of approximately $(3x310 + 3x280) \times 85\% \times 85\% \approx 1280$ patients completing this study.

Open-label treatment period with memantine (substudy):

With a sample size of n=100 the upper 1-sided 90% confidence limit for 0 to 10 AEs observed is:

Number of AEs	0	1	2	3	4	5	10
observed							
Upper 1-sided CI	2.3%	3.9%	5.3%	6.6%	7.9%	9.1%	15.0%
for AE incidence							

This is regarded as sufficient accuracy for evaluating safety and tolerability.

16.12 Statistical Analysis Plan

A Statistical Analysis Plan describing the handling of data issues and the planned statistical analyses in more detail will be prepared by the Department of Biostatistics, H. Lundbeck A/S, before any of the lead-in studies are unblinded.

17 Clinical Study Report and Publications

17.1 Clinical Study Report

Upon completion of the study, a *Clinical Study Report* will be prepared by the Department of Medical Writing, H. Lundbeck A/S.

17.2 Data Ownership

The data collected in this study are the property of Lundbeck.

17.3 Publications

The results of this study will be submitted for publication.

The primary publication based on this study must be published before any secondary publications are submitted for publication.

Authors of the primary publication must fulfil the criteria defined by the *International Committee of Medical Journal Editors (ICMJE)*.²¹

18 Indemnity and Insurance

In the event of study-related injuries or deaths, insurance for the patients and indemnity of the investigators and those of their employees, servants, or agents whose participation in this study has been documented are provided. Insurance and liability will be in accordance with applicable laws and *Good Clinical Practice*.³

19 Finance

19.1 Site Agreement

The financial agreements for the site are addressed in one or more documents. Both parties must sign the agreements before the site is initiated.

19.2 Financial Disclosure

All the investigators, including sub-investigators and raters, participating in the study must complete a *Financial Disclosure Form* in order to comply with the United States Food and Drug Administration (FDA) *Financial Disclosure* requirements.

Appendix II

Recent and Concomitant Medication: Disallowed or Allowed with Restrictions

Recent and Concomitant Medication: Disallowed or Allowed with Restrictions

In the table below disallowed recent and concomitant medications are listed, including any restrictions with respect to their use prior to and during the study.

Disanowed Recent and Concomitant Medication		
Drug Class	Details	
Any investigational drug	Disallowed throughout the whole study.	
AChE inhibitors or cholinergic	All AChE inhibitors except donepezil are disallowed. Treatment with	
agonists or antagonists	donepezil must have been stable at 10 mg/day and must be maintained	
	throughout the duration of the study.	
Anti-cholinergic drugs acting on	Allowed only if prescribed for urinary and bladder difficulties, including	
the muscarinic acetylcholine	frequent urination and inability to control urination. Dose modifications and	
receptor	initiation of treatment are disallowed during the study.	
Anaesthetics:		
General	General anaesthetics are disallowed during the study except in case of	
Local	emergency procedures requiring anaesthesia.	
	Episodic use of local anaesthetics is allowed.	
Analgesics	Codeine and tramadol are allowed. Other opioid analgesics are disallowed	
	during the study.	
Anorexics	Disallowed during the study.	
Antiacne agents	Disallowed during the study.	
	Agents for topical use are allowed.	
Antiarrhythmics	Open-label treatment period (initial 28-week period):	
	Flecainide and propafenone disallowed. For other antiarrhythmics dose	
	modifications and initiation of treatment are allowed during the study. As	
	specified in the donepezil SPC precaution should be taken when administering	
	quinidine.	
	Open-label treatment period with memantine (substudy):	
	Flecainide, quinidine and propafenone disallowed. For other antiarrhythmics	
	dose modifications and initiation of treatment are allowed during the study.	
	Procainamide is allowed but caution should be exercised according to the	
	memantine SmPC.	
Antibiotics	Disallowed for chronic use during the study.	
	UTI prophylaxis with antibiotics is allowed.	
Anticoagulants	Low dose Low Molecular Weight Heparins for deep vein thrombosis	
-	prophylaxis are allowed. The anti-aggregation agents clopidogrel, or aspirin,	
	or dipyridamole are allowed. Other anticoagulants are disallowed during the	
	study.	
Anticonvulsants	Disallowed if indication is epilepsy or convulsions.	
	Pregabalin is allowed for treatment of neuropathic pain. Gabapentin is allowed	
	for treatment of neuropathic pain or essential tremor. Treatment must be well	
	tolerated and the dose must have been stable during the study with no	
	modification of the dose. Initiation of treatment during the study is disallowed.	
	All other anti-epileptic agents are disallowed during the study, regardless of	
	the indication.	

Dicall лЪ 4 C • 4 nt Madiaati .

Drug Class	Details
Antidepressants	Stable treatment with no modification of dose with selective serotonin reuptake inhibitors (SSRIs), venlafaxine, moclobemide and mirtazapine for the duration of the study. Paroxetine and duloxetine should be used with caution. Initiation of treatment not allowed during the study. Trazodone (maximum evening dose of 50 mg) is acceptable if the treatment is stable. Initiation and dose modification are not allowed during the study. Other antidepressants are disallowed. As specified in Section 4.5 of the donepezil SmPC precaution should be taken when administering fluoxetine.
Antidiarrhoeal agents	Allowed except opioid-containing agents.
Antifungal agents:	
Systemic	Systemic antifungal agents are disallowed during the study.
Topical	Antifungal agents for topical use are allowed.
Antihistamines	Only fexofenadine, (dex)loratidine and cetirizine allowed throughout the study.
Antihypertensives	Centrally active antihypertensives (such as clonidine, alphamethyldopa, guanidine, gaunfacine, moxonidine) are disallowed. For all other
	antihypertensives, dose modifications and initiation of treatment are allowed during the study.
Anti-impotence agents	Disallowed during the study.
Antinauseants	Occasional use for up to five consecutive days allowed.
Antineoplastics	Disallowed during the study.
Antiobesity agents	Disallowed during the study.
Anti-parkinson agents (e.g., levodopa, dopamine agonists, COMT inhibitors, amantadine, monoamine oxidase B	Disallowed during the study.
inhibitors anticholinergies etc)	
Anti-psoriatic agents	Disallowed during the study.
1 0	Anti-psoriatic agents for topical use are allowed.
Antipsychotics depot	Disallowed during the study.
Antipsychotics typical	Disallowed during the study.
Antipsychotics atypical	Only treatment with risperidone (maximum 2 mg/day) or quetiapine (maximum 100 mg/day) is allowed if absolutely necessary, and if prescribed according to treatment guidelines. Risperidone or quetiapine treatment should not be initiated within 3 days of a study visit with efficacy assessments.
Antiviral agents	Anti-HIV agents are disallowed.
Anxiolytics	The use of benzodiazepines as anxiolytic treatment is acceptable, provided the
	dose remains fixed during the study. Where absolutely necessary,
	benzodiazepine treatment can be initiated as a short-term anxiolytic treatment
	during the study, as long as the treatment is not initiated within 3 days of a
	study visit with efficacy assessments.
	Use of antidepressants is described in the corresponding row.
Benign prostate hyperplasia	Only alpha-1 blockers (Terazosin, Tamsulosin, Doxazosin) and finasteride are
Beta-blockers	Precaution should be taken when administering betablockers
Cough/cold agents	Onen-label treatment period (initial 28-week period):
Cough cold ugents	Only non-opioids and codeine allowed.
Diuretics	Open-label treatment period with memantine (substudy): Only non-opioids and codeine allowed. Dextromethorphan disallowed. Open-label treatment period with memantine (substudy): Hydrochlorothiazide and triamterene are disallowed.

Drug Class	Details		
H2 blocker/proton pump	Open-label treatment period (initial 28-week period):		
inhibitors	Dose modifications and initiation of treatment allowed during the study.		
	Open-label treatment period with memantine (substudy):		
	Dose modifications and initiation of treatment allowed during the study, but		
TT ' 1 1' 1	caution should be exercised according to the memantine SmPC.		
Hormones, including hormone-	Dose modifications and initiation of treatment allowed during the study.		
replacement therapy	Steroids: See separate row.		
Hormone suppressants	Dose modifications and initiation of treatment allowed during the study.		
Insulin	Rosiglitazone is disallowed.		
Hypolipidaemics	Dose modifications and initiation of treatment allowed during the study.		
Muscle relaxants	Allowed on a p.r.n. basis (not to exceed 5 consecutive days).		
	As specified in Section 4.5 of the donepezil, rivastigmine and galantamine		
	SmPC precaution should be taken when administering neuro-muscular		
	blockers.		
NMDA-antagonist (memantine)	Open-label treatment period (initial 28-week period):		
	Disallowed during the study.		
	Open-label treatment period with memantine (substudy):		
	NMDA receptor antagonists, except for memantine, are disallowed (e.g.,		
Develo stropic o conta not	Disellowed during the study		
etherwise specified (including	Disallowed during the study.		
harbal aganta)	Gingko Biloba is allowed provided the dose remains fixed during the study.		
Sedatives/	Zalnidem zalenlan and zaniclone: These selected hymnotics are accentable		
hyphotics	provided the dose remains fixed during the study. Melatonin is allowed		
nyphotes	anytime. Where absolutely necessary, these agents may be initiated during the		
	study as long as the treatment is not initiated within 3 days of a study visit with		
	efficacy assessments		
	Please refer to Anxiolytics for benzodiazepines.		
Steroids:			
Systemic	Systemic steroids are disallowed during the study.		
Topical	Topical and inhalant use allowed before and throughout the study.		
Inhalant			
Urinary alkalinizers	Open-label treatment period with memantine (substudy):		
	Disallowed for patients participating in the open-label treatment period with		
	memantine (substudy) (e.g. carbonic anhydrase inhibitors, sodium		
	bicarbonate)		

Appendix IV

Lead-in Study Treatment Designs

Lead-in Study Treatment Designs

Study	IMP	Base treatment
	Idalopirdine (30 mg)	
14861A	Idalopirdine (60 mg)	Donepezil hydrochloride (10 mg)
	РВО	
	Idalopirdine (10 mg)	
14862A	Idalopirdine (30 mg)	Donepezil hydrochloride (10 mg)
	РВО

SDTM Standard Data Tabulation Model

Page 6 of 48

LU Study Number: 14861B Pluto ID: CLI 00933680

Status: Final

Version: 1.0

Trial Site Number: Study Level

SOC system organ class

TEAE treatment-emergent adverse event

ULN upper limit of normal

LU Study Number: 14861B Pluto ID: CLI_00933680

Status: Final Version: 1.0

Trial Site Number: Study Level

1 Objectives

1.1 Primary Objective

Open-label treatment period:

To evaluate the long term safety and tolerability of idalopirdine as adjunctive therapy to donepezil in patients with mild-moderate AD.

Open-label treatment period with memantine (sub-study):

To evaluate the safety and tolerability of concomitant treatment with idalopirdine, memantine and donepezil in patients with mild-moderate AD.

1.2 Secondary Objective

Open-label treatment period:

To evaluate the long-term disease development during treatment with idalopirdine as adjunctive therapy to donepezil in patients with mild-moderate AD.

Open-label treatment period with memantine (sub-study):

To evaluate the disease development during concomitant treatment with idalopirdine, memantine and donepezil in patients with mild-moderate AD.

1.3 Other Objectives

Open-label treatment period with memantine (sub-study):

To explore population pharmacokinetics.

2 Study Design

This is an interventional, multi-national, multi-site, open-label extension study in patients with mild to moderate AD who completed the 24-week "lead-in" double-blind, placebo controlled clinical studies 14861A and 14862A (from now on these studies will be referred to as "lead-in study" in the document). Randomized, blinded treatment in lead-in study will remain blinded to sites, CRAs, patients, and investigators until patients have completed the extension study (the sponsor will generally be un-blinded after unblinding of 14861A and 14862A occurs).

LU Study Number: 14861B Trial Site Number: Study Level Pluto ID: CLI 00933680

[figure not shown]
Patients completing the open-label treatment period and who will not continue into the 24-week open-label memantine sub-study (described below) will enter a 4-week safety follow-up period. Thus the total study duration of the open-label treatment period per patient from Baseline II (Visit 1 of the open-label treatment period and Visit 7 of the lead-in study) to the end of the follow-up will be approximately 32 weeks.

Some sites will be participating in the open-label treatment period with memantine (substudy). In total, 100 patients who have completed the open-label treatment period will be recruited for the for the memantine sub-study. For these patients, the study will include two consecutive periods:

- Open-label treatment period (initial 28-week period): 28-weeks with idalopirdine 60 mg/day as adjunctive treatment to donepezil (10 mg/day). The dose of idalopirdine can be decreased to 30 mg/day if 60 mg/day is not well tolerated in the opinion of the investigator. The Baseline Visit of this period (Baseline II) will be the same visit as Visit 7 (Completion Visit) in the lead-in studies.

• Adverse events (AEs)

LU Study Number: 14861B Trial Site Number: Study Level Pluto ID: CLI 00933680

- Clinical safety laboratory tests
- Vital signs
- Weight
- Electrocardiograms (ECGs)
- Columbia Suicide Severity Rating Scale (C-SSRS)

Other endpoints

• Plasma concentrations of idalopirdine and memantine in the open label treatment period with memantine

4 Analysis Sets

The following analysis set will be used to analyse and present data:

The sets of patients to be analysed are defined as follows:

Open label treatment period

- all-patients-enrolled set (APES) all patients enrolled in the open-label treatment period
- *all-patients-treated set* (APTS) all patients in APES who took at least one dose of IMP in the open-label treatment period

Open label treatment period with memantine

- *all-patients-enrolled set 2* (APES2) all patients who enrolled in the open-label treatment period with memantine
- *all-patients-treated set 2* (APTS2) all patients in APES2 who took at least one dose of IMP or memantine in the open-label treatment period with memantine.

Each patient will be classified according to these definitions based on information in data, and no Classification Meeting will be held.

If not otherwise specified, tables, figures, and listings will be based on the APTS for the open-label treatment period, and on APTS2 for the open-label treatment period with memantine.

5 Descriptive Statistics

Unless otherwise specified, summary statistics (n, arithmetic mean, standard deviation [SD], median, lower and upper quartiles, minimum and maximum values) will be presented for continuous variables, and counts and, if relevant, percentages will be presented for categorical variables.

Tables and figures for the open label treatment period will be presented by lead-in treatment group and in total.

LU Study Number: 14861B Trial Site Number: Study Level Pluto ID: CLI 00933680

Unless otherwise specified, data listings will include lead-in treatment group (placebo or idalopirdine [dose 10mg, 30mg, or 60mg]), site, patient screening number (from lead-in study), and lead-in study-Baseline I information on sex, age, race, and weight.

6 Patient Disposition

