
Safety Assessments

- Adverse events (AEs)
- Clinical safety laboratory tests
- Vital signs
- Weight/Body Mass Index (BMI)
- Electrocardiograms (ECGs)
- Physical and neurological examinations
- Columbia Suicide Severity Rating Scale (C-SSRS)

Endpoints

N/A

Statistical Methodology

The following analysis sets will be used to analyse and present data:

- all-patients-treated set (APTS) all patients who took at least one dose of IMP in the open-label treatment period (initial 28-week period).
- all-patients-treated set 2 (APTS2) all patients who took at least one dose of both IMP and memantine in the open-label treatment period with memantine (substudy).

All analyses in the open-label treatment period (initial 28-week period) will be based on the APTS, and all analyses in the open-label treatment period with memantine (substudy) will be based on APTS2.

Safety and efficacy assessments will be summarised descriptively. On an exploratory basis the development of efficacy assessments in the open-label treatment period (initial 28-week period) will be analysed using Mixed Models for Repeated Measurements (MMRM).

Data will be presented for each treatment period [open-label-treatment period (initial 28-week period) and open-label treatment period with memantine (substudy)] separately for all patients in total as well as by treatment group (placebo or idalopirdine all doses pooled) in the lead-in study, or by lead-in study, and treatment group in the lead-in study.

Sample Size Considerations

Open-label treatment period (initial 28-week period):

The study will include eligible patients who have completed Visit 7 (Completion Visit) of the lead-in studies. Assuming a completion rate of 85% and that approximately 85% of these are eligible and complete the extension study, this results in a total of approximately $(3x310 + 3x280) \times 85\% \times 85\% \approx 1280$ patients completing this study.

Open-label treatment period with memantine (substudy):

With a sample size of n=100 the upper 1-sided 90% confidence limit for 0 to 10 AEs observed is:

Number of AEs	0	1	2	3	4	5	10
observed							
Upper 1-sided CI	2.3%	3.9%	5.3%	6.6%	7.9%	9.1%	15.0%
for AE incidence							

This is regarded as sufficient accuracy for evaluating safety and tolerability.

Ethical Rationale for Study and Study Design

Patients will be fully informed about the study including the risks and benefits of his/her participation in the study.

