6.7 Post-study Access to IMP

Open-label treatment period (initial 28-week period):

The patients will not be provided with IMP or donepezil hydrochloride after study completion. The patient must be treated in accordance with normal clinical practice and may continue on donepezil hydrochloride as per prescription, if judged relevant by the investigator.

Open-label treatment period with memantine (substudy):

The patients will not be provided with IMP or donepezil hydrochloride after study completion. The patient must be treated in accordance with normal clinical practice and may continue on donepezil hydrochloride and/or memantine as per prescription, if judged relevant by the investigator.

7 Concomitant Medication

For patients in the open-label treatment period (initial 28-week period): Concomitant medication is any medication other than the IMP and donepezil that is taken during the study.

For patients in the open-label treatment period with memantine (substudy): Concomitant medication is any medication other than the IMP, and donepezil and memantine that is taken during the study.

The concomitant medications that are disallowed during the study are summarised in Appendix II.

Data on concomitant medications that are on-going at V7 (Completion Visit) of the lead-in study will be transferred to the 14861B study. Any changes, including reason for the change, in concomitant medication must be recorded at each subsequent visit. For any concomitant medication initiated or for which the dose has changed due to a new disorder or worsening of a concurrent disorder, the disorder must be recorded as an adverse event.

8 Study Visit Plan

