6.1 Summary of Patient Disposition

Patient disposition in the open label-treatment period will be summarised by lead-in study and in total, and include the number of patients in each analysis set defined for the period, and the number of patients in the APTS who completed or withdrew from treatment. The corresponding summary will be generated for the open-label treatment period with memantine for the total study.

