Exposure to IMP in each treatment period will be summarised using descriptive statistics, and include the patient years of exposure (PYE). PYE will be calculated as the sum of the number of days of exposure to IMP for each patient, divided by 365.25 days.

In addition, exposure to IMP in each treatment period will be categorised into day intervals. The intervals for the open-label treatment period are the following: $(1-28\ [0-1\ month], 29-56\ [1-2\ months], 57-84\ [2-3\ months], 85-126\ [3-4.5\ months], 127-168\ [4.5-6\ months], 169-252\ [6-9\ months].$ The intervals for the open-label treatment period with memantine are the following: $(1-168\ [0-6\ months], 169-252\ [6-9\ months], 253-364\ [9-12\ months], 365-448\ [12-15\ months])$. Missing values of exposure will not be imputed.

Number and percentage of patients with dose reduction of IMP to 30 mg/day in the open-label treatment period will be summarised. The mean dose of IMP will be calculated for each patient and summarised (mean, median, and lower and upper quartiles). Categorical summaries of patients' dosage at each visit will be presented as well.

LU Study Number: 14861B Trial Site Number: Study Level Pluto ID: CLI 00933680

10 Efficacy

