11.1.4 Allocation of TEAEs to Treatment Periods

TEAEs will be allocated to treatment periods according to the time of onset of the adverse event:

• *adverse event in the open-label treatment period* – an adverse event that starts or increases in intensity after the date of Baseline II and at or before the date of the last protocol-

LU Study Number: 14861B Trial Site Number: Study Level Pluto ID: CLI 00933680

- specified contact in the study for patients not continuing into the open-label treatment period with memantine, and at or before the date of Baseline III for patients in the APES2.
- adverse event in the open-label treatment period with memantine an adverse event that starts or increases in intensity after the date of Baseline III and at or before the date of the last protocol-specified contact in the study.

Note, the completion Visit in the lead-in studies are the same as the Baseline II Visit in the extension study, and adverse events ongoing or starting at Baseline II and not increasing intensity will only be reported in the lead-in study.

All tables and listings will be presented separately for adverse events in the open label treatment period, and the open label treatment period with memantine.

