11.1.5 All Adverse Events

All adverse events will be listed for the APES and APES2.

An overview of the PYE, numbers, and percentages of patients with TEAEs, serious adverse events (SAEs), adverse events leading to withdrawal, or patients who died will be provided. For TEAEs, SAEs, and adverse events leading to withdrawal, the total number of events will be included.

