Plasma concentrations of idalopirdine and memantine will be summarised descriptively for the APTS2 in the open-label treatment period with memantine.

13 Health Economic Analyses

The health economic assessments conducted during the open-label treatment period (RUD Lite, EQ-5D-3L and Dependence scale) in the open-label will be summarised by lead-in study. For the open label treatment period, absolute scores, change from Baseline I scores, and change from Baseline II will be summarised by visit week. The summaries of absolute scores and change from Baseline I scores will include data from the lead-in study and the open-label treatment period.

For the open label treatment period with memantine, absolute score and change from Baseline III in MMSE total score will be summarised by visit week.

14 Interim Analyses

No interim analyses planned.

Page 23 of 48 Trial Site Number: Study Level

LU Study Number: 14861B Pluto ID: CLI_00933680 Status: Final

Version: 1.0

15 Sample Size Considerations

Open-label treatment period:

The study will include eligible patients who have completed Visit 7 (Completion Visit) of the lead-in studies. Assuming a completion rate of 85% and that approximately 85% of these are eligible and complete the extension study, this results in a total of approximately $(3x310 + 3x280) \times 85\% \times 85\% \approx 1280$ patients completing this study.

Open-label treatment period with memantine (sub-study):

With a sample size of n=100 the upper 1-sided 90% confidence limit for 0 to 10 AEs observed is:

Number of AEs observed	0	1	2	3	4	5	10
Upper 1-sided CI for AE incidence	2.3%	3.9%	5.3%	6.6%	7.9%	9.1%	15.0%

This is regarded as sufficient accuracy for evaluating safety and tolerability.

16 Data and Analysis Standards and Statistical Software

The data will be collected and analysed in accordance with the Lundbeck standards specified in Lundbeck SDTM, Version 3.1.2 or later, SADs, Version 5.1 or later, and TGML, Version 7.0 or later.

The statistical software used will be SAS®, Version 9.4 or later.

17 Changes to Analyses Specified in the Protocol

C-SSRS will be summarized as worst case per treatment period rather than worst case per visit. However, all C-SSRS results for the study will be listed for those patients that experience any suicidal ideation or behaviour.

18 Details on Data Handling

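### The SAP widens the substudy analysis set APTS2 from patients who took both idalopirdine and memantine to those who took either, and narrows the basis for listings, without declaring either change

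*SAP*

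**What the plan says.** **Protocol.** The synopsis and section 16.2 define APTS2 in the same words: "all patients who took at least one dose of both IMP and memantine in the open-label treatment period with memantine (substudy". Section 16.2 bases all substudy analyses on that set, but bases listings on all patients who enter the treatment period.

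**SAP.** Section 4 defines APTS2 as "all patients in APES2 who took at least one dose of IMP or memantine in the open-label treatment period with memantine". It makes APTS2 the default for substudy tables, figures and listings alike. One stated exception concerns adverse events (section 11.1.5): "All adverse events will be listed for the APES and APES2". Section 12 also uses APTS2 for the plasma concentration summaries.

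**Declared changes.** Section 17 of the SAP lists one change from the protocol: "C-SSRS will be summarized as worst case per treatment period rather than worst case per visit". It mentions neither the APTS2 definition nor the basis for listings, and no other part of the SAP gives a reason for them.

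**Purpose of the substudy.** The primary objective (protocol section 2.1, SAP section 1.1) is the safety and tolerability of idalopirdine, memantine and donepezil given together.

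**The concern.** Protocol section 6.1 has every substudy entrant continue the idalopirdine dose from the 28-week period. A condition met by either drug is therefore met by almost everyone enrolled, and the memantine part of the definition does nearly no work. A patient who enrols, continues idalopirdine and never takes memantine would count in the denominator of the tables that are to describe the combination.

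A reader of the planned summary tables could not see this:

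- Disposition (SAP 6.1) will "include the number of patients in each analysis set defined for the period", and under the SAP definition that count mixes patients who took both drugs with those who took one.
- Exposure (SAP section 9) covers the IMP alone: "Exposure to IMP in each treatment period will be summarised using descriptive statistics".
- Memantine is outside the concomitant medication tables, since protocol section 7 says for the substudy: "Concomitant medication is any medication other than the IMP, and donepezil and memantine that is taken during the study".
- Memantine dosing appears only in a listing (SAP section 8).

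The report would then rest on a set that differs from the protocol's under the same name, without saying so. The SAP also drops the protocol's Classification Meeting, so membership follows directly from the SAP wording.

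**Working it through.** **1. The two definitions.** Divide APES2 (everyone enrolled in the substudy) by what was taken after entry.

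| Taken in the substudy period | Protocol APTS2 | SAP APTS2 |
|---|---|---|
| Both IMP and memantine | in | in |
| IMP only | out | in |
| Memantine only | out | in |
| Neither | out | out |

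The SAP set always contains the protocol set. They are equal only if nobody took just one drug.

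**2. How many patients this concerns.** The documents give no figure. Three provisions of the protocol make it probably small: the investigator must judge that memantine is required (5.3, substudy inclusion 7), patients likely to interrupt or stop memantine are excluded (substudy exclusion 7), and first doses of both drugs are due the day after Visit 6 (6.1).

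**3. The plan's own precision figures.** Protocol 16.11 and SAP section 15 give upper one-sided 90% limits for n = 100. The exact limit U solves P(X ≤ x | n, U) = 0.10, so U is the 0.90 quantile of Beta(x + 1, n − x). For x = 0, 1, 2, 3, 4, 5 and 10 this gives 2.28, 3.83, 5.23, 6.56, 7.83, 9.08 and 14.99%. Rounded up to the next 0.1, all seven agree with the stated 2.3, 3.9, 5.3, 6.6, 7.9, 9.1 and 15.0%. None of these figures depends on which definition is used.

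**4. Illustration (k and j are assumptions).** Let 100 patients enrol and all take IMP, and let k never take memantine. Ten patients with a given event are among the 100 − k who took both, and j are among the k. Then:

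- protocol set: incidence = 10 / (100 − k)
- SAP set: incidence = (10 + j) / 100

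| k | Protocol set | SAP set, j = 0 | Exact upper limit, 10 events in 100 − k |
|---|---|---|---|
| 0 | 10/100 = 10.0% | 10.0% | 15.0% |
| 2 | 10/98 = 10.2% | 10.0% | 15.3% |
| 5 | 10/95 = 10.5% | 10.0% | 15.8% |
| 10 | 10/90 = 11.1% | 10.0% | 16.6% |

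The direction is not fixed. At k = 5, j = 1 gives 11/100 = 11.0% and j = 2 gives 12.0%, against 10.5% in the protocol set. The SAP figure is the higher one whenever j/k exceeds 10/(100 − k).

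**5. Precision.** With 95 patients instead of 100, the upper limit for 0 events moves from 2.28% to 2.39%, and for 10 events from 14.99% to 15.75%. About 0.5 of that 0.8-point rise is the higher point estimate (10.53 − 10.00 = 0.53). The SAP does not plan these limits as output.

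**The case against.** An inclusive treated set is a normal choice for safety, and here it has a practical advantage. SAP 11.1.4 ends the first period "at or before the date of Baseline III for patients in the APES2". Under the SAP definition, a patient who continues idalopirdine without memantine stays in the substudy tables. Under the protocol definition, that patient's events after Baseline III would be in the summary tables of neither period. This stands: the wider set is defensible, provided that it is declared and explained.

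The effect may also be nil. The entry rules make zero non-starters plausible, and with about 100 patients the memantine dosage listing should let a careful reader find any that exist. This stands too, and it limits the size of the point, although it leaves the reader to rebuild the protocol's set by hand.

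A reader might infer more than the documents support:

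- **That combination safety will be materially understated.** No number of non-starters is given, and the difference can go either way.
- **That the protocol definition secures real concomitant exposure.** It asks for one dose of each drug, so it removes non-starters and no more.
- **That restoring it would hide liver signals.** The listing in SAP 11.3.3 of patients with liver values above the upper limit of normal is based on APTS, which contains every entrant treated in the 28-week period under either definition.
- **That the memantine concentration summary is seriously affected.** The SAP flow chart includes sampling at Visit 6, before the first memantine dose, so pre-memantine samples exist under either definition.

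**Conclusion.** The inconsistency is certain. The protocol requires both drugs, the SAP accepts either, the basis for listings has also changed, and section 17 declares neither. Followed as written, the SAP gives a default set that can include patients never exposed to the combination named in the primary objective, and no summary table would show how many.

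The numerical effect is unknown and probably small. On the assumptions above, with no events among non-starters, it is 0.2 points at k = 2 and 1.1 points at k = 10 for an event seen in 10 patients. It is zero if every entrant takes both drugs. The substudy is descriptive, so no test decision depends on it. The point should be fixed because the definition is undeclared and bears on the primary objective, not because a material bias has been shown.

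**What to change.** Either of two routes resolves it, and they are equally sound.

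**A. Return to the protocol.** In SAP section 4, define APTS2 for the substudy tables as APES2 patients with at least one dose of both IMP and memantine in that period. Base all substudy listings on APES2, as protocol 16.2 requires, so that patients who took one drug stay visible for adverse events, laboratory tests, vital signs, weight, ECGs, C-SSRS, exposure, withdrawals and memantine dosing. For these patients, list IMP exposure explicitly, because the SAP plans days on idalopirdine only in the listing of withdrawn patients.

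**B. Keep the wider set.** Declare it in SAP section 17 with a reason, and repeat the key safety tables for patients who took both drugs.

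**Under either route:**

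- In SAP 6.1, report how many APES2 patients took both drugs, IMP only, memantine only, or neither.
- State how a patient with missing memantine dosing records is classified. Memantine is prescribed and not supplied by the sponsor (protocol 6.2), and SAP 18.4.1 deals with missing dates for the IMP only.
- Declare in section 17 any basis for listings that still differs from the protocol.

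**Cost.** The data are already to be collected. Route A may bring the table denominator slightly below 100 and changes the population for several listings. Route B needs a few extra tables. The separate counts or listings may turn out to hold few patients or none.
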